#### 5.7.3.6 Lung Function Parameters

*Lung function parameters* (observed and % predicted FVC, observed and % predicted FEV1, absolute and predicted FEV1/FVC ratio and observed and % predicted DLCO) and changes from the inclusion visit will be presented for all scheduled visit with descriptive statistics.

The DLCO value will be reported in either traditional units (mL/min/mmHg) or SI units (mmol/min/kPa). Values in SI units can be multiplied by 2.987 to obtain values in traditional units (Graham et al., 2017).

#### 5.7.3.7 Flare-ups

The number of flare-ups since the last visit (for post-inclusion visits) as well as the number of participants with investigator-reported flare-ups, number of intercurrent flare-ups, location of flare-ups, flare-up causes, flare-up symptoms, flare-up outcomes (restricted movement and bone formation) and flare-up duration will be presented for each scheduled visit by body location and overall with descriptive statistics. For the summary of flare-ups, percentages will be calculated using the number of participants with at least a flare-up at each visit as the denominator. The following body locations will be presented:

- Shoulder (Includes left and right shoulder)
- Elbow (Includes left and right shoulder)
- Wrist or Hand (Includes left wrist or hand and right wrist or hand)
- Hip (Includes left hip and right hip)
- Knee (Includes left hips and right hip)
- Ankle or Foot (Includes left ankle or foot and right ankle or foot)
- Back (Includes upper back and lower back)
- Chest
- Abdomen
- Head and Anterior neck
- Jaw and Submandibular Area
- Spine (Includes Cervical Spine, Thoracic Spine and Lumbar Spine)
- Other (Includes all other locations)

The number of flare-ups since the last visit will be calculated by totalling the number of distinct flare-ups (based upon the flare-up start dates, not including intercurrent flare-ups) using the visit windows as defined in section 6.1.

Duration of flare-up will be defined as (date of end of flare-up – date of start of flare-up + 1) and will be calculated for each distinct flare-up before summing across each participant.

An intercurrent flare-up is defined as a new flare-up or marked worsening of the original flare-up at any time during a flare-up based treatment cycle.

In addition, the total number of flare-ups across the study, the duration of study participation, the individual flare-up rate per month and the global flare-up rate (including the 95% confidence interval derived using a poisson model offset by the duration of study participation) across all participants per month will be summarised.

The individual flare-up rate per month will be defined as  $[(\text{Number of flare-ups during study follow-up}) / \text{duration in the study (in months)}]$ . This duration will be calculated as  $(\text{end of study date} - \text{informed consent date} + 1) / 30.4375$ .

The global flare-up rate will be calculated as the sum of flare-ups across all participants / sum of durations in the study(months).

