9.4 Statistical Analyses

9.4.1 *General Considerations*

Statistical evaluation will be performed using Statistical Analysis System (SAS[®]) (Version 9.4 or higher).

No formal statistical testing will be performed. All the analyses will be primarily descriptive in nature. If p-values are presented, they will be for exploratory purposes only.

For descriptive analyses, summary statistics will be presented at each scheduled visit and will include sample size, number of available observations (N), number of missing observations (missing), mean, 95% CIs of the mean/median, standard deviation (SD), number of nonmissing observations (n), median and range for continuous variables and scores. For categorical or discrete variables, the absolute and relative (percentage) numbers based on the nonmissing number of observations for each category will be presented, including 95% CIs.

Missing data will not be replaced but will be displayed in all relevant tables.

The Inclusion Visit is the first study visit (Day 1) and first administration of palovarotene in Study CLIN-60120-452 (and corresponds to the EOS Visit of the parent study for assessments already performed in the parent study).

All analyses will be performed by parent study (PVO-1A-301 or PVO-1A-202/PVO-1A-204), by palovarotene status at the time of transition to Study CLIN-60120-452 (treated, not treated) and treatment regimen (chronic treatment only, flare-up treatment only, chronic & flare-up treatment) and overall.

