### **5.1.2 Descriptive Statistics**

All raw and derived variables will be listed and described using summary statistics.

For descriptive analyses, summary statistics will be presented at each scheduled visit and will include sample size, number of available observations (n), number of missing observations

(missing), mean, 95% CIs of the mean/median, standard deviation (SD), median and range for continuous variables. For categorical or discrete variables, the absolute and relative (percentage) numbers based on the non-missing number of observations for each category will be presented, including 95% CIs.

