#### **A4. Programming Convention for Outputs**

All text fields must be left justified and numeric or numeric with some text specification (e.g.: not done, unknown, <4.5, ...) must be decimal justified.

The mean, median, lower quartile, upper quartile, SD and standard errors (SE) of the mean/median 95% confidence interval values will be reported to one decimal place greater than the raw data recorded in the database.

The minimum and maximum values will be reported with the same number of decimal places as the raw data recorded in the database.

In general, the maximum number of decimal places reported should be four for any summary statistic.

Percentages will be presented to one decimal place. Percentages will not be presented for zero counts. Percentage will be calculated using n as denominator. The denominator n will be specified in a footnote for clarification if necessary. If sample sizes are small, the data displays will show the percentages, but in the CSR only frequency counts should be described.

All values below or above a limit of detection (e.g. <0.1 or >100) will be listed as such.

Dates will be presented in the format [ddmmmyyyy] and times in the format [hh:mm].

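### The per-visit flare-up table takes its occurrence percentages only over participants who flared, and its Elbow and Knee rows are defined as shoulders and hips

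*SAP*

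**What the plan says.** The items in SAP 5.7.3.7 include "the number of participants with investigator-reported flare-ups, number of intercurrent flare-ups, location of flare-ups", together with causes, symptoms, outcomes and duration. They "will be presented for each scheduled visit by body location and overall with descriptive statistics". The next sentence sets one rule for the whole summary: "percentages will be calculated using the number of participants with at least a flare-up at each visit as the denominator". No item is exempted.

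The general rule in SAP 5.1.2 for categorical variables is "the absolute and relative (percentage) numbers based on the non-missing number of observations for each category will be presented, including 95% CIs". Protocol 9.4.1 has the same rule: "the absolute and relative (percentage) numbers based on the nonmissing number of observations for each category will be presented, including 95% CIs". SAP Appendix A4 adds "Percentage will be calculated using n as denominator", and says that zero counts carry no percentage. SAP 2.6, which records changes from the protocol's statistical section, lists only the reduced set of subgroups.

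The location list in 5.7.3.7 contains "Elbow (Includes left and right shoulder") and "Knee (Includes left hips and right hip"). The Shoulder and Hip rows are already defined by those same joints. The last row, Other, takes every location not named elsewhere.

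**The concern.** Whether a participant flared in a window is a yes/no observation on everyone followed in that window. Dividing the number who flared by itself says nothing about how common flare-ups were. Dividing the number with a hip flare-up by the number with any flare-up gives the make-up of the flare-ups, and that figure moves whenever flare-ups elsewhere become more or less frequent. The same applies within each treatment-regimen column, because SAP 5.1.1.1 splits every summary table by regimen.

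Flare-ups at each follow-up visit, by location and overall, are a stated secondary endpoint. A reader of the table will take a percentage beside participants with flare-ups as the share of treated participants. The location breakdown has a separate fault: under the printed definitions, two joint rows repeat two others.

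**Working it through.** The plan states no figure to reproduce, because there is no sample-size or power calculation. The check applies the printed rules. Flare-up counts are assumed, since the documents give none. N = 87 is the enrolment maximum (SAP 2.3), and N = 60 is an assumed smaller number followed. Intervals are Clopper-Pearson 95%.

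**1. Overall occurrence row.** Let k be the participants with at least one flare-up in the window and N the participants followed. The SAP rule gives k/k; the share of participants is k/N.

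| k | SAP rule (95% CI) | k/87 (95% CI) | k/60 (95% CI) |
|---|---|---|---|
| 5 | 100% (47.8–100) | 5.7% (1.9–12.9) | 8.3% (2.8–18.4) |
| 10 | 100% (69.2–100) | 11.5% (5.7–20.1) | 16.7% (8.3–28.5) |
| 20 | 100% (83.2–100) | 23.0% (14.6–33.2) | 33.3% (21.7–46.7) |
| 40 | 100% (91.2–100) | 46.0% (35.2–57.0) | 66.7% (53.3–78.3) |

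At k = 0 the SAP ratio is 0/0. Appendix A4 would leave that percentage blank.

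**2. By-location rows.** Let L be the participants with a flare-up at one location. The rule gives L/k, which is N/k times L/N. With L = 5 for the hip:

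- k = 10: 5/10 = 50.0%
- k = 20: 5/20 = 25.0%
- k = 40: 5/40 = 12.5%
- share of participants in all three cases: 5/87 = 5.7%

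The hip figure falls fourfold while the number with a hip flare-up stays the same. These rows are not forced to 100%.

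**3. Location definitions taken literally.** Take 24 made-up flare-ups, each at one joint: shoulder 7, elbow 3, hip 9, knee 5.

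| Row | True | As defined |
|---|---|---|
| Shoulder | 7 | 7 |
| Elbow | 3 | 7 |
| Hip | 9 | 9 |
| Knee | 5 | 9 |
| Other | 0 | 3 + 5 = 8 |
| Sum | 24 | 40 |

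The excess is 40 − 24 = 16, which is the 7 shoulder and 9 hip events counted a second time. The overall row is not affected.

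**4. Which denominator fits the numerator.** SAP 5.7.3.7 assigns flare-ups to windows by start date. Suppose a participant misses the Month 6 visit and reports at Month 12 a flare-up that began on Day 100. Day 100 lies in the Month 6 window (Days 2–274, SAP 6.1), so the event enters the Month 6 numerator. A denominator of participants assessed in that window would leave this person out; one of participants under observation in the window would include them.

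**The case against.** Several points on the other side stand.

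- **A conditional denominator is right for part of the table.** Cause, symptom and outcome exist only where there is a flare-up. A flare-up denominator for those rows is reasonable and arguably agrees with the non-missing-observations rule in 5.1.2. The fault is in extending it to occurrence.
- **Change over time is not hidden.** A reader might infer that a doubling in the share who flare would vanish from the report. The documents do not support that. SAP 5.1.2 requires absolute numbers and sample size, 5.2 tabulates participants per visit, and 5.7.3.7 also gives the number of flare-ups since the last visit. An approximate proportion can be worked out by hand. The individual and global monthly rates use all participants, but for the whole study and not by visit.
- **Bone growth is largely covered elsewhere.** A reader might also infer that bone formation among treated participants cannot be followed. SAP 5.7.3.8 gives a per-visit percentage of participants with extra bone growth, with no flare-only denominator. Its wording leaves open whether growth with and without a flare-up is shown separately, as protocol 9.4.3.8 plans. Restricted movement has no all-participant percentage anywhere.
- **The shells are a separate document.** The occurrence row may turn out to show a count only. However, descriptive statistics under 5.1.2 mean count, percentage and interval. If only a count appears, no per-visit proportion is specified at all.
- **Elbow and Knee look like copying slips.** The row labels are right, and a programmer may follow them. Then the correction would be silent, and the SAP would not describe the table produced.
- **The endpoint is worded as numbers, outcomes and duration,** not as a proportion who flare. That limits the weight of the point, but it does not make a percentage fixed at 100% useful.

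**Conclusion.** The point holds in a limited form. The overall occurrence percentage, if printed, is 100% whenever anyone flared. By-location percentages are inflated by N/k relative to the share of treated participants: 8.7-fold for k = 10 and N = 87 (87/10). Restricted movement lacks any percentage over all participants. The two location definitions are wrong as written, and no other section corrects them.

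The rest of the flare-up reporting remains usable. It would be wrong to conclude that every percentage in the table is 100%, or that the secondary endpoint cannot be evaluated. The analysis is descriptive, so no test, error rate or sample size is affected.

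The sizes rest on assumed flare-up counts and an assumed number followed. The 100% result follows from the rule alone, provided a percentage is shown. The double counting depends on the location definitions being programmed literally.

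**What to change.** In SAP 5.7.3.7:

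1. For participants with a flare-up, overall and by location, use as denominator the FAS/SAS participants under observation in that visit window. Define this as having study follow-up within the window, so that it matches the assignment of flare-ups by start date. Print this N in the table.
2. Keep participants with at least one flare-up as the denominator for causes, symptoms and outcomes, and label those percentages as conditional on having flared. If an all-participant percentage for restricted movement is wanted, add one row on the denominator in item 1.
3. Define Elbow as left and right elbow, and Knee as left and right knee.

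The cost is SAP wording and one table shell. The flare-up data are already collected. The change is best made before database lock, since SAP section 1 requires later deviations to be documented in the study report.

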1.3 Schedule of Activities

The schedule of activities (SoA) planned in this study are presented in [Table 1](#).

Table 1 Schedule of Activities

Assessment/Procedure	Inclusion Visit[a] Day 1			Follow-Up Visits Every 6 months (± 1 month)[b]/ EOS/EW Visit[c]	
	Procedures already performed at the parent EOS Visit that will be transferred from parent study database	Procedures already performed at the parent EOS Visit to be entered in CLIN-60120-452 eCRF by the study site	Procedures to be performed at the CLIN-60120-452 Inclusion Visit	In-clinic Visit	Remote visit
Informed consent[d]			X		
Inclusion/exclusion criteria			X		
Study intervention administration/accountability[e]			X	X	X
Baseline demographics			X		
Physical examination			X		
Participant interview[f]			X		
Pregnancy testing and childbearing potential [g]		X[a]*		X	X
Linear height and body weight [h]		X[a]*		X	X
Vital signs [i]		X[a]*		X	X
Spinal health assessment [j]		X [a]**		X	
Lung function assessments [k]			X	X	
Flare-up assessment [l]			X	X	X [m]
Additional Extra bone growth assessment (without associated flare-up)			X	X	X
CAJIS [n]	X*			X	X
C-SSRS [n] [o]			X	X	X
FOP-PFQ assessment[p] [q]	X*		X [q]***	X	X
PROMIS Global Health Scale [p][q]	X*		X [q]***	X	X
FOP assistive devices assessment [p]			X	X	X
Healthcare Utilization [p]			X	X	X
Biochemistry (amylase, lipase, AST, ALT) and triglycerides	X*				
Disease and flare-up history	X				
Prior medications	X				
Concomitant medications		X		X	X
Concomitant procedures [r]		X		X	X
AEs [s]		X		X	X

AE=adverse event; ALT=alanine aminotransferase; AST=aspartate aminotransferase; CAJIS=Cumulative Analogue Joint Involvement Scale for FOP; COVID-19=coronavirus disease 2019; C-SSRS=Columbia-Suicide Severity Rating Scale; DLCO=diffusion capacity of the lung for carbon monoxide; eCRF=electronic case report form; EOS=End of Study; EW=Early Withdrawal; FEV₁=forced expiratory volume in one second; FVC=forced vital capacity; FOP=fibrodysplasia ossificans progressiva; FOP-PFQ=FOP Physical Function Questionnaire; PROMIS=Patient Reported Outcomes Measurement Information System.

a. The Inclusion Visit should be in-clinic and corresponds ideally to the EOS Visit of the parent study (Study PVO-1A-301 or PVO-1A-202/PVO-1A-204). A maximum of one month is allowed between the two visits. For any assessments

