Symptoms of a flare-up typically include, but are not limited to, localised pain, soft tissue swelling/inflammation, redness, warmth, decreased joint range of motion and stiffness. Only one symptom is required to define a flare-up. Flare-ups can occur in the absence of any apparent causative factor, but there is a high risk that substantial traumatic events (e.g. surgery, intramuscular immunisation, mandibular blocks for dental work, muscle fatigue, blunt muscle trauma from bumps, bruises, falls or influenza-like viral illnesses) can lead to a flare-up and result in heterotopic bone formation.

At each visit, the investigator will ask the participant if they experienced any flare-ups since their last visit, the location of the flare-ups, the start and stop date or whether it is ongoing, if any flare-up concomitant medication was taken and whether the flare-up resulted in extra bone growth and/or restricted movement. When extra bone growth occurred, the location will be specified and the investigators will ask the participant how the extra bone growth affected their movement.

Bone growth, loss of mobility and audiology impact that occurs as a consequence of a flare-up will be reported as an AE or SAE (see Section 10.3.1).

8.1.8 *Extra Bone Growth Assessment (without associated flare-up)*

For each extra bone growth (without associated flare-up) the location of the extra bone growth, whether it was preceded by injury, illness, vaccination and/or other events (“yes”, “no” or “unknown”), extra bone growth start date, duration and whether it is ongoing, will be collected at the Inclusion Visit and Follow-up/EOS/EW Visits.

At each visit, the investigator will ask the participant if they experienced any extra bone growth (without associated flare-up) since their last visit and the details of these extra bone growths.

8.1.9 *Qualitative Participant Interviews*

In-depth qualitative interviews will be proposed to all participants and will be conducted in person or by telephone by the PI/qualified site staff. Interviews can be carried out anytime within 1 year (ideally within 1 month) following the Inclusion Visit with consenting participants.

Participants will be asked to describe her/his past experience with FOP (e.g. symptoms, joint being locked) and with palovarotene (e.g. decrease in number of flare-ups, delay in physical disability, overall satisfaction).

Participants will also be asked to describe:

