#### *5.1.1.3 Presentation of Visits / Timepoints*

Summaries by visit will be presented using the derived window visits (See Section 6.1). Visits in the TFLs will be presented as follows and in the following order:

Visit Name
Baseline
Month 6
Month 12
Month 18
Month 24
Month 30
Month 36

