#### 5.7.3.8 *Extra Bone Growth*

The percentage of participants with any extra bone growth (associated or not with a flare-up) since the previous visit will be presented for each visit with descriptive statistics. The number of extra bone growths since the previous visit will be calculated by totalling the number of distinct records (based upon the start date) within each of the visit windows as defined in section 6.1.

The location (and associated restricted movement if collected), the cause/proceed by, the number preceded by symptoms and the duration of bone growth will be presented in a listings. The duration of the bone growth will be defined as  $(\text{date of end of bone growth} - \text{date of start of bone growth} + 1)$ .

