## **6 DATA HANDLING**

### **6.1 Visit window**

The below time windows for visit/timepoints will be used for analyses:

Analysis Visit	Scheduled Day	Visit Window
Baseline	Up to Day 1	≤ Day 1 Last non-missing measurement taken prior to first Investigational Medicinal Product (IMP) administration in study CLIN-60120-452
Month 6	182	Day 2-274
Month 12	365	Day 275-456
Month 18	547	Day 457-639
Month 24	730	Day 640-821
Month 30	912	Day 822-1003
Month 36	1095	≥ Day 1004

For post-baseline visit windows, the following applies when there are multiple assessments in a particular visit window, the closest to the scheduled day is chosen (if two assessments have the same distance, then the later one will be chosen).

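### By-visit counts of flare-ups and extra bone growths use nearest-visit windows of 273 then 182 days, so they fall by a third from Month 6 to Month 12 at a constant event rate

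*SAP*

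**What the plan says.** SAP 5.7.3.7 gives this rule for flare-ups: "The number of flare-ups since the last visit will be calculated by totalling the number of distinct flare-ups". Each flare-up is placed by its start date, intercurrent flare-ups are left out, and the totals are formed "using the visit windows as defined in section 6.1". SAP 5.7.3.8 labels its count as running from the previous visit and totals distinct bone-growth records by start date "within each of the visit windows as defined in section 6.1".

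SAP 6.1 assigns Day 2–274 to Month 6, Day 275–456 to Month 12, Day 457–639 to Month 18, Day 640–821 to Month 24, Day 822–1003 to Month 30, and Day 1004 onward to Month 36. Its stated purpose is selection: when several assessments fall in one window, "the closest to the scheduled day is chosen". SAP 5.1.1.3 adds a general rule: "Summaries by visit will be presented using the derived window visits".

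Data collection follows a different interval. Protocol 8.1.7 says: "At each visit, the investigator will ask the participant if they experienced any flare-ups since their last visit". Protocol 8.1.8 says: "At each visit, the investigator will ask the participant if they experienced any extra bone growth (without associated flare-up) since their last visit". Protocol Table 1 schedules follow-up visits six months apart, with a tolerance of one month either way.

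**The concern.** A nearest-visit window suits a point measurement such as CAJIS or FOP-PFQ, where one value per window is kept. An event count is different, because it grows with the time over which events are counted. The Month 6 window has no earlier post-baseline window to share days with. It therefore starts at Day 2 and runs to the midpoint between the Month 6 and Month 12 visits, well past the Month 6 visit itself.

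Two things follow. The Month 6 count covers a longer period than any later one, and its content does not match its label. With on-time visits, an event starting between Day 183 and Day 274 lies after the Month 6 visit and before the Month 12 visit, yet it is tabulated under Month 6.

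Protocol Table 3 asks for flare-up results and the share of participants with extra bone growth at each follow-up visit. There is no comparator arm, and nothing in either document adjusts the by-visit tables for window length. A reader who sees fewer events at Month 12 than at Month 6 could take this for a change in the disease when only the length of the window has changed.

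**Working it through.** **Inputs.** Windows and scheduled days (182, 365, 547, 730, 912, 1095) come from SAP 6.1. The three-year maximum, November 2021 to November 2024, comes from Protocol 4.1.

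**Reproducing the windows.** Midpoints between consecutive scheduled days are 273.5, 456, 638.5, 821 and 1003.5. The stated upper limits are 274, 456, 639, 821 and 1003, so the table is a correct set of midpoint windows.

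**Length as a counting period** (last day − first day + 1):

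| Visit | SAP 6.1 window | Days | Interval ending on the scheduled day | Days |
|---|---|---|---|---|
| Month 6 | 2–274 | 273 | 2–182 | 181 |
| Month 12 | 275–456 | 182 | 183–365 | 183 |
| Month 18 | 457–639 | 183 | 366–547 | 182 |
| Month 24 | 640–821 | 182 | 548–730 | 183 |
| Month 30 | 822–1003 | 182 | 731–912 | 182 |
| Month 36 | 1004 onward | varies | 913 to end of study | varies |

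**Mean counts.** At constant rate r the expected count is r × length, so r cancels in the ratio. Month 12 over Month 6 is 182/273 = 0.667, a fall of 33.3%, for participants followed through Day 456. Counts then stay flat to Month 30. With intervals ending on the scheduled days the ratio is 183/181 = 1.011, a change of +1.1%.

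**Earlier exits.** Suppose a fraction d leaves at Day 182 and a fraction e at Day 365, and each window's mean is taken over those who enter it. Mean days at risk are 273 − 92d for Month 6 and 182 − 91e/(1 − d) for Month 12.
- d = 10%, e = 0: 263.8 and 182.0 days, a fall of 31.0%.
- d = e = 20%: 254.6 and 159.3 days, a fall of about 37.5%.
- Extremes with each fraction between 0 and 20%: 28.5% (d = 20%, e = 0: 254.6 and 182.0 days) and 40.0% (d = 0, e = 20%: 273 and 163.8 days).

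**Month 36.** This window depends on each participant's follow-up. If the study ends on 30 November 2024 (an assumption; the documents give only the month), a participant with Day 1 on 1 December 2021 reaches Day 1096 and contributes 1096 − 1004 + 1 = 93 days. One with Day 1 on 3 March 2022 reaches Day 1004 and contributes 1 day. The documents do not say how many get that far, so no single fall is claimed.

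**Events placed under a different visit from the one that follows them.** The share of the interval between the Month 6 and Month 12 visits that is tabulated under Month 6 is:
- visits on Day 182 and 365: Day 183–274, 92/183 = 50.3%;
- both 30 days early: Day 153–274, 122/183 = 66.7%;
- both 30 days late: Day 213–274, 62/183 = 33.9%.

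**Percentage with any extra bone growth.** The SAP states the 6.1 rule only for the number of growths. If the same windows also define the percentage, and events follow a Poisson process, the percentage is 1 − exp(−r × days/365.25). The documents give no rate, so a range is shown:

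| Assumed rate per year | Month 6 (273 days) | Month 12 (182 days) | Relative fall |
|---|---|---|---|
| 0.25 | 17.0% | 11.7% | 31% |
| 0.5 | 31.2% | 22.1% | 29% |
| 1 | 52.6% | 39.2% | 25% |
| 2 | 77.6% | 63.1% | 19% |

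With intervals ending on the scheduled days, the two values at 0.5 per year are 21.9% and 22.2%.

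**The case against.** The study is descriptive and single-arm, all affected outputs are secondary, and the windows themselves are correctly derived. SAP 5.7.3.7 already plans individual and global monthly flare-up rates over the whole study, the global one with a duration offset, and these do not use the windows. By-visit flare-up percentages are taken among participants with a flare-up at that visit, so they do not scale with window length. The by-visit bone-growth result named for presentation is a percentage, to which the 33.3% does not apply. Flare-ups are reported to the site as they occur, so assigning them by start date is sensible. Visit-to-visit intervals would themselves vary in length. The distortion could also work the other way: set against the six-month bone-growth history in SAP 5.4, a 273-day Month 6 window makes early on-study results look worse.

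Much of this stands as a limit on scope. The fault is one of definition and labelling, not a miscalculated window, and placing events by start date is not in question. But a whole-study rate does not correct a by-visit table, and bone growth has no planned rate at all. SAP 5.1.2 calls for all derived variables to be summarised, which covers the bone-growth count. In a descriptive study the by-visit table is itself the result. The unequal length of real visit intervals is a reason to show person-time, not a reason to keep 6.1.

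**Conclusion.** The concern holds. Followed as written, the SAP produces by-visit counts over periods of 273, 182, 183, 182 and 182 days, while describing them as counts since the last or previous visit.

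- **Directly affected:** by-visit numbers of flare-ups and of extra bone growths. The 33.3% fall needs no assumed rate value, only a constant rate and follow-up through Day 456; assumed exits of up to 20% at each of two visits leave a fall of 28.5% to 40.0%.
- **Affected only if the same windows are applied:** the number of participants with a flare-up, summed flare-up duration, and the percentage with any extra bone growth. SAP 5.1.1.3 makes this the likely reading, but it is not stated. For the percentage, the fall is 19% to 31% at assumed rates of 2 down to 0.25 per year.
- **Not affected:** whole-study individual and global flare-up rates, and the primary TEAE analysis.

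This should be fixed before database lock, by which time SAP section 1 requires the plan to be final. It does not threaten the primary objective.

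**What to change.** Keep SAP 6.1 for point measurements only. In 5.7.3.7 and 5.7.3.8:

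1. Replace the reference to 6.1 with actual visit-to-visit intervals, which match the questions asked under Protocol 8.1.7 and 8.1.8. State how each interval is labelled, including one that closes with an early-withdrawal visit or spans a missed visit.
2. If that is not practicable, use intervals ending on the scheduled days: Day 2–182, 183–365, 366–547, 548–730, 731–912, and 913 to end of study.
3. State that the same intervals apply to the number of participants with a flare-up, summed flare-up duration and the percentage with any extra bone growth.
4. Show person-time at risk, or events per person-month, beside each by-visit count, so that unequal or incomplete intervals are visible. Early, late and missed visits and the last interval all need this.

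A whole-study bone-growth rate, parallel to the one for flare-ups, would be a useful option but is not essential. The cost is SAP wording and minor programming on dates already collected.
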